#### 6.7 – Missing data and sensitivity analysis

Subjects who miss a study visit should be contacted immediately by the Investigational site to determine the reason for the missed visit and to reschedule the visit as soon as possible to meet the study visit window. If the subject cannot be located after 3 attempts by phone, email and/or letter, then the subject will be considered lost to follow-up. All attempts to contact the subjects will be documented and retained in the subject study record.

With regard to the main judgement criteria, data will be censored if the patient is lost to follow-up (death, disability, relocation, or drop-out).

As the burden of study participation does not differ between the tailored and the anatomical arm, we expect all study losses to be non-differential with respect to treatment assignment. Thus, our results will not be biased as a result of these losses.

Additional supportive analyses will be performed on the primary endpoint to assess the effect of missing data.

For missing demographic data, the data will not be replaced because it has no weight on the main judgment criterion.

A rigorous monitoring is expected, any missing data will be filled in during these visits.

	CLIPL-01-002-E	CONFIDENTIAL
	CLINICAL INVESTIGATION PLAN	F 09 XX 01 Rev.A Page 35/47

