#### 5.2.3 – Criteria and procedures for withdrawal or termination of a subject's participation

A patient's participation ends if any of the following occurs:

- At the end of 12-month follow-up period or if relevant, after resolution of a study-device-related adverse event ongoing at the time of the 12-month follow-up
- If the patient does not undergo an AF catheter ablation
- At any time, in the event of withdrawal of consent or cooperation by the patient
- At any time, if the patient is lost to follow-up
- At any time, in the event of patient's exclusion from the study, required for safety reasons according to the investigator's judgement
- In the event of the patient's death
- At any time, in the event of withdrawal of approval from relevant Ethics Committee or IRB

In each of the above termination cases, the appropriate case report form must be completed to document and justify the end of a patient's participation in the study.

If an adverse effect due to the implementation of the protocol is observed, the study may be suspended at any time by the sponsor.

Premature termination of the study may occur motivated by a general decision (Ethics Committees, IRBs, regulatory Competent Authorities, Data Safety Monitoring Board) for safety reasons related to the use of the device or study procedures.

A site may be terminated for the following reasons: failure to comply with the conditions of the study protocol and/or failure to accurately complete case report forms.

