#### 5.3.5 – Trans Telephonic event Monitor (TTM)

All patients will receive a portable ECG device (KardiaMobile, AliveCor) that they will keep throughout their participation in the Study. They will be asked to perform one 30-second ECG recording per week, and whenever they have arrhythmia symptoms. All TTM recordings will be automatically uploaded in a secured platform for blind review by the ECG core lab.

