## **VI – STATISTICAL CONSIDERATIONS**

### **6.1 – Design, statistical methodology and analytical procedures**

Standard summary statistics will be calculated for all study variables (demographics and outcomes) by study group and for all patients. For continuous variables, statistics will include means, standard deviation and 95% confidence intervals for means when assumptions of normal distribution are not violated. Median and quartiles may also be presented. Categorical variables will be summarized using frequency distributions.

The analysis for the primary endpoint will be a modified Intention-To-Treat (mITT) analysis, allowing exclusion of some randomized subjects in a justified way:

- Patients that are deemed ineligible after randomization or that do not have any AF ablation will be excluded
- Patients in the Tailored group for whom AF cannot be induced and who undergo conventional ablation will be included in this analysis
- Patients lost to follow-up (death, disability, relocation, or drop-out) during the 3-month blanking period will be excluded
- Patients who complete at least their 3-month follow-up but who are lost to follow-up (death, disability, relocation, or drop-out) before the 12-month follow-up will be included in the analysis and the data will be censored
- Patients who undergo a 3rd ablation procedure (re-repeat procedure) will be included in the analysis but the data will be censored at the time of the 3rd procedure.

A per-protocol (PP) population will also be evaluated and will serve as supportive analyses to the mITT analysis. In the PP analysis, the population will be analyzed according to the treatment actually received at the start of the study, and will consist of patients that met all the inclusion criteria, none of the exclusion criteria, were successfully treated, had no important protocol deviations and attended all the scheduled follow-up visits.

 <small>ARTIFICIAL INTELLIGENCE SERVING HEART DISEASE</small>	CLIPL-01-002-E	CONFIDENTIAL
	CLINICAL INVESTIGATION PLAN	F 09 XX 01 Rev.A Page 33/47

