4.1.2 The Modified Intent-to-Treat Population (mITT)

The modified Intention-To-Treat (mITT) set will include all randomized subjects except for:

- Subjects who are deemed ineligible after randomization or who do not have any AF ablation, and
- Subjects lost to follow-up during the 3-month blanking period.

Subjects in the Tailored group for whom AF cannot be induced and who undergo conventional ablation will be included in the mITT analysis.

Subjects who complete at least their 3-month follow-up visit but who are lost to follow-up before the 12-month follow-up visit will be included in the mITT analysis.

Subjects who undergo a 3rd ablation procedure will be included in the analyses but the data will be censored at the time of the 3rd procedure for multiple procedure endpoints.

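### Failed contact after a missed visit ends participation and, if dated within blanking, removes the patient from the primary set, although endpoint-window rhythm data may exist or be obtainable

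*Protocol*

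**What the plan says.** Protocol 6.7 and SAP 6.3 carry the same rule. After a missed visit the site contacts the patient at once "to reschedule the visit as soon as possible to meet the study visit window". Then: "If the subject cannot be located after 3 attempts by phone, email and/or letter, then the subject will be considered lost to follow-up". No spacing between attempts is set.

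That status has two consequences:

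- **Participation.** Protocol 5.2.3 opens its list with "A patient's participation ends if any of the following occurs", and one item is "At any time, if the patient is lost to follow-up".
- **Primary set.** SAP 4.1.2 removes from mITT "Subjects lost to follow-up during the 3-month blanking period". Protocol 6.1 words it as "Patients lost to follow-up (death, disability, relocation, or drop-out) during the 3-month blanking period will be excluded". Later losses are treated differently. SAP 4.1.2 states "Subjects who complete at least their 3-month follow-up visit but who are lost to follow-up before the 12-month follow-up visit will be included", and their data are censored.

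Rhythm data do not depend only on visits. Under protocol 5.3.5 the patient makes one recording a week, and more when symptomatic. "All TTM recordings will be automatically uploaded in a secured platform for blind review by the ECG core lab".

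**The concern.** Whether a patient counts in the primary analysis should turn on whether rhythm was, or could be, observed between months 3 and 12. Under these rules it can turn on whether the site reached the patient around a visit that contributes nothing to that window.

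Three things are at stake:

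- A randomised and ablated patient may be left out of the primary comparison for a post-randomisation reason unrelated to the availability of outcome data.
- If participation ends, later rhythm and safety data may not be collected. Protocol 5.3.8 handles a third procedure differently: efficacy data are censored, but the patient remains in the study for safety.
- Both documents argue that losses cannot bias the result because the burden of participation is equal in the two arms. Equal burden does not make loss independent of recurrence. The supportive missing-data analyses are promised but not described. The only sensitivity analysis listed for the primary endpoint (SAP 4.2.4) uses the per-protocol set.

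**Working it through.** **The plan's own figures.** From protocol 6.2, HR = ln(0.77)/ln(0.62) = 0.547. A log-rank calculation (Lakatos method, exponential survival, no accrual period, one-sided 0.025) gives 80.0% power at N = 292, as stated. 292/0.78 = 374.4 against the stated 374, and 374 × 0.22 = 82.3 against the stated 82. These figures reproduce and are not in question.

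**Timing.** Inputs are protocol Table 8 (visit windows) and SAP 6.2 (one month = 30.4 days; blanking = 98 days).

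- The 3-month visit window runs from 2 × 30.4 + 1 = day 61.8 to 3 × 30.4 = day 91.2. Protocol 5.3.6 requires the Holter within the same window.
- Blanking ends at day 98, so the whole 3-month assessment falls inside it.
- From the close of the visit window to the end of blanking is 98 − 91.2 = 6.8 days.

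**mITT membership after a missed 3-month visit.** The result depends on a date that neither document defines.

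- If loss is dated to the missed visit, or to a third failed attempt by day 98, it falls within blanking and the patient is excluded.
- If loss is dated to a third failed attempt after day 98, the exclusion does not apply. The clause that protects later losses does not apply either, because the 3-month visit was not completed. SAP 4.1.2 starts from all randomised subjects and then lists exceptions, so the patient would stay in.
- If loss is dated to the last rhythm recording, the patient is in or out according to when the last TTM strip arrived.

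Two otherwise identical patients can therefore be classified differently according to how quickly a site makes three attempts.

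**Can endpoint data exist without visits?** Yes. SAP section 5 counts AF on one weekly TTM transmission, confirmed by a second on a different day of the same week or in the next week, as primary-endpoint failure. No visit is needed.

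**Comparison with the per-protocol rule.** SAP 4.1.3 accepts one missed Holter if TTM compliance exceeds 50%. A patient whose only missed assessment is at month 3 could meet that attendance test and still be excluded from mITT if recorded as lost within blanking.

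**What one patient forfeits.** The endpoint window is 365 − 98 = 267 days. An early exclusion forfeits all of it. For a patient declared lost around the 6-month visit (nominal day 6 × 30.4 ≈ 182; window closing at about day 212), the forfeited share is (365 − 212)/267 = 57% to (365 − 182)/267 = 69%. This holds only if the patient is censored at that date and later recordings are not used, and the documents say neither.

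**Power.** Losses within the 22% allowance cost no planned power. If, as an assumption, 4, 8, 19 or 37 patients (about 1%, 2%, 5% or 10% of 374) were lost beyond that allowance, power would fall from 80.0% to 79.5%, 78.9%, 77.3% or 74.5%. The documents give no count of such patients.

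**The case against.** The strongest reply is that much of the harm is read into silence. A reader might infer that the patient is lost permanently, even if TTM uploads continue or the patient returns. The documents do not say so. They contain no rule against re-entry and no instruction to ignore later uploads. The test is also that the patient cannot be located, which is stricter than not answering, and a patient who uploads every week may not meet it.

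A reader might also infer that missing the 3-month visit always removes the patient from mITT. That is not established, because it depends on the undefined date. Protocol 6.1 glosses loss as death, disability, relocation or drop-out, which does not plainly include failed contact. After a completed 3-month visit the consequence is censoring, not removal. Out-of-window follow-up is a deviation, but it is not on the list of important ones in protocol 10.2.

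On safety, SAP 4.1.1 keeps every randomised patient who had a first ablation, and Method 1 in SAP 4.5 offsets for time on study. Data already collected are therefore kept. What is at risk is data not yet collected when participation ends.

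These points stand and limit the finding. They do not remove it. A site and statistician who follow protocol 5.2.3, protocol 6.7 and SAP 4.1.2 as written can still end follow-up and drop a patient whose endpoint data exist or could be obtained.

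**Conclusion.** The concern holds in a limited form, and the text should be changed. The rules allow a randomised, ablated patient to be dropped on visit or contact status while endpoint-window rhythm data exist or could be obtained. They also leave mITT membership after a missed 3-month visit undetermined, so it could be settled after data are seen.

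The size per patient is clear: an early exclusion forfeits the full 267-day window. The total is not. The number of such patients is not in the documents, so neither the bias nor its direction can be computed.

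A reader might expect a definite gain in power from recovering these patients. The documents do not support a figure. The 22% allowance includes patients never ablated, whom follow-up contact cannot recover. Patients lost after month 3 already contribute censored time. No shortfall against planned power is shown.

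The conclusion assumes that failed contact counts as loss under SAP 4.1.2 and that protocol 5.2.3 is applied as written.

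**What to change.** 1. In SAP 4.1.2 and protocol 6.1, exclude for early loss only patients with no rhythm recording (TTM, Holter or ECG) after day 98. Keep any patient already counted as failing at 3 months because of a repeat procedure during blanking (SAP 6.2).
2. In protocol 6.7 and SAP 6.3, record a missed visit with failed contact as a missed visit. Keep the patient on TTM and re-contact at each later window. Assign loss to follow-up only when the 12-month window closes (12 × 30.4 + 30, about day 395), and censor at the last rhythm recording.
3. Amend protocol 5.2.3 so that failed contact alone does not end participation.

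The cost is wording and a few extra contact attempts, with no new procedure or device. One drawback is that some patients will be followed on sparse TTM, possibly triggered by symptoms, which could over-detect recurrence. A sensitivity analysis can check this, for example by censoring such patients at their last attended assessment or by using the planned analysis without TTM. Another is that rule 1 still conditions on behaviour after randomisation, but a patient with no recording after day 98 has no observed rhythm in the endpoint window to contribute.

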## 6.8 – Minimum and maximum number of subjects to be included for each site

A maximum of 75 inclusions per site (20% of inclusions) will be allowed in order to prevent site-effect. This limit will ensure a minimum of 5 enrolling sites.

## 6.9 – Poolability of Sites

All investigational sites will follow the requirements of standardized data collection procedures and forms. The primary efficacy and safety endpoints will be presented separately for each site using descriptive statistics. Poolability of the primary efficacy endpoint across investigational sites will be evaluated using a logistic regression model with a fixed effect for site. If there is a significant effect of site, analysis will be repeated using site as a random effect. Sites enrolling fewer than 5 subjects will be combined to form one quasi site. Additional exploratory analyses may be performed to understand any variations in outcome by site. Assessment of poolability by geography (US vs. OUS) will be performed based on logistic regression as described above. As US subjects will only be patients with AF duration of 3 months to < 12 months, only OUS patients with AF <12 months will be included in the poolability by country assessment. As only one catheter type is approved for use in the US, an additional subgroup analysis of each catheter used will assess the variability, if any, by country for patients with the same catheter type.

## VII – RISKS DESCRIPTION AND MINIMIZATION

### 7.1 – Expected clinical benefits

VX1 offers a fast and reliable way to identify patient-specific spatio-temporal dispersion EGMs. Previous research done by Volta suggests that consistently targeting dispersed EGMs has resulted in less recurrence of AF. In addition, research by Volta Medical has shown that targeting of dispersed electrograms identified by VX1 results in lesser surface area ablated than targeting complex fractionated atrial electrograms (CFAEs). In targeting these dispersed electrograms in addition to conventional approaches, patients may benefit from fewer redo AF ablation procedures and less recurrence of atrial arrhythmias.

### 7.2 – Expected adverse effects of the device

The use of VX1 is not expected to increase the likelihood of any adverse effect that might otherwise occur during a cardiac ablation. Use of the VX1 device has been characterized by longer mapping time than observed in comparable patient populations in literature, however procedure times and ablation time have not shown to be longer. Complications associated with AF ablation procedures are well-documented and anticipated. Risks for cardiac ablation include, but are not limited to those identified in section 14.3 – Anticipated adverse events.

### 7.3 – Risks associated with participation in the clinical investigation

Subjects randomized into the Tailored arm of the study are expected to receive higher RF times, greater ablation area, and slightly longer procedure times than subjects randomized to the anatomical arm. However, previous research indicates that RF time, ablation area, and procedure time while using the VX1 system are well within accepted industry standards for AF ablation and consistent with other approaches to AF ablation in published literature. The study design assumes that all patients receive the standard of care and expect additional benefits linked to close and repeated follow-ups after AF ablation.

The procedures and methods for data collection required by the protocol do not differ from routine AF ablation and post-ablation follow-up practice, other than filling out a Quality-of-Life questionnaire at baseline and at each follow-up visit.

	CLIPL-01-002-E	CONFIDENTIAL
	CLINICAL INVESTIGATION PLAN	F 09 XX 01 Rev.A Page 36/47

Use of the device not in conformance with this investigational plan and/or with the instructions in the physician's manual could introduce other issues.

#### **7.4 – Measures to control or mitigate risks**

To protect the welfare of subjects, Ethics Committee or IRB approval of the investigation will be obtained for each site prior to the first case at that site.

Investigators selected to participate in this study will have experience in AF ablation. Trained and experienced clinical and technical personnel representing Volta Medical will be made available to support procedures and for troubleshooting.

All areas recommended for ablation by the VX1 system will be reviewed by the investigator, and if the investigator determines that the recommended region is undesirable for ablation the investigators will be instructed to maintain the subject's safety first and avoid ablation of undesirable regions. The frequency of such divergent assessments will be documented and evaluated.

Each investigator will sign an Investigator Agreement stating his/her responsibility to conduct this study according to this investigational plan, to adhere to the records and reporting requirements, and to supervise use of the device.

Through careful design and testing, Volta Medical has attempted to minimize the risk to patients. Testing included: software validation testing, electrical safety and electromagnetic compatibility testing according to IEC 60601 standards on the hardware system.

VX1 Application has received CE mark on 14 JAN 2020, VX1 Hardware has received CE mark on 09 JUL 2020.

Copy of the CE certificates are in Appendix 18.3.

Volta Medical Quality Management System is ISO 13485 certified.

#### **7.5 – Justification of the risk-benefit ratio**

Considering the potential risks, the measures taken to minimize risks and the potential benefit to patients, the risk-benefit ratio is deemed acceptable for the use of VX1 and for the conduct of this study.

### **VIII – DATA MANAGEMENT**

Electronic Data Capture (EDC) will be used for this investigation for collecting the data. The EDC/eCRF system will be managed by Labcorp according to Labcorp standards. Confidentiality of patient identity will be ensured.

A complete detailed guideline on data to be recorded for the study and how to fill in the eCRFs will be provided to the Investigators.

Data will be reviewed and cleaned, as well as data queries issued and resolved, in accordance with the Data Management Plan.

Audits or inspections by Competent Authorities and FDA may be carried out.

 <small>ARTIFICIAL INTELLIGENCE SERVING HEART DISEASE</small>	CLIPL-01-002-E	CONFIDENTIAL
	CLINICAL INVESTIGATION PLAN	F 09 XX 01 Rev.A

## **IX – AMENDMENTS TO THE CLINICAL INVESTIGATION PLAN**

Major changes to the protocol will be described in a Clinical Investigation Plan Amendment. The amendment will identify the changes made, the reason for the changes and if it is mandatory or optional to implement the amendment.

The principal investigator will acknowledge the receipt of the amendment and confirm by their signature on the Amendment Signature page that they will adhere to the amendment.

The amendment must be submitted to the relevant Ethics Committees or IRB and to Authorities, where required. Approval from the Ethics Committees or IRB will be required prior to implementation of the amendment.

Any amendment affecting the patient requires that the patient be informed of the changes and a new consent be signed and dated by the investigator and patient prior to the patient's next follow-up.

Changes to, or formal clarifications of, the clinical investigational plan will be documented in writing and provided to investigators. This information will be incorporated when an amendment occurs.

## **X – DEVIATIONS FROM CLINICAL INVESTIGATION PLAN**

### **10.1 – General**

A protocol deviation is defined as any event where the clinical investigator or site personnel did not conduct the study according to the protocol.

The Investigator is not allowed to deviate from the Clinical Investigation Plan.

In emergency situations, deviations from the Clinical Investigation Plan, established in order to protect the rights, safety and well-being of the subjects, may be carried out without authorization of Volta Medical or Ethics Committee/IRB prior approval. Such deviations should be recorded and forwarded as soon as possible to Volta Medical and the appropriate Ethics Committee or IRB.

In particular, every effort should be made to avoid deviations from the protocol including, but not limited, to the following:

1. Inclusion of a patient without appropriate written consent or who does not meet the inclusion criteria or who meets any of the exclusion criteria,
2. Missing any data related to the primary and secondary endpoints,
3. Use of other energy than RF for ablation (cryo/chemical),
4. Ablation other than antral PVI in the Anatomical arm for index procedures (e.g. lines other than ICT, EGM ablation, PV encirclement other than antral),
5. Ablation other than PVI ± lines (as defined in 5.3.7 – Redo procedure) in the Anatomical arm for redo procedures,
6. Failure to terminate AF with incomplete mapping in the Tailored group (mono atrial mapping, too short mapping < 20 minutes),
7. Failure to terminate AF with incomplete ablation in the Tailored group, leaving dispersion areas not ablated, without valid justification (for safety reasons at operator's discretion),
8. Failure to terminate AF without a mandatory second mapping/ablation cycle in the Tailored group,
9. Patient becoming unblinded to his/her randomization assignment,
10. Follow-up being performed outside the time window allowed.

 <small>ARTIFICIAL INTELLIGENCE SERVING HEART DISEASE</small>	CLIPL-01-002-E	CONFIDENTIAL
	CLINICAL INVESTIGATION PLAN	F 09 XX 01 Rev.A

